11.3 Subject privacy

11.4 Data disclosure

11.5 Data safety and monitoring

11.6 Risk/benefit

11.6.1 Potential study risks

11.6.2 Potential study benefits

11.6.3 Risk/benefit assessment

## **1. Abstract**

Regular physical activity is associated with reduced risk of cardiovascular disease, diabetes, hypertension, and obesity. Despite these benefits, more than half of adults in the United States do not achieve enough physical activity to obtain these benefits. Moreover, nearly 70% of Americans are overweight or obese and could benefit from greater physical activity. Many stakeholders are increasingly interested in using digital health approaches to increase physical activity including using wearable devices to monitor activity and using engagement strategies such as gamification to change behaviors. However, the evidence on these approaches is limited. Social incentives, the influences that impact individuals to adjust their behaviors based on social ties or connections, are ubiquitous and could be leveraged within gamification interventions to provide a scalable, low cost approach to increase engagement. Gamification, or the use of game design in non-game situations, is commonly used in the real world, but in most cases has not appropriately leveraged principles from theories of health behavior. By incorporating insights from behavioral economics, these approaches could be designed to anticipate predictable barriers to behavior change. In this study, we will test the effectiveness of three social incentive-based gamification interventions to increase physical activity using a 24-week intervention period with a 12-week follow-up.

## **2. Overall objectives**

The objective of this study is to use a randomized, controlled trial to test the effectiveness of three interventions using social incentives and gamification to increase physical activity among overweight and obese adults.

## **3. Aims**

### *3.1 Primary outcome*

The primary outcome is change in daily steps from baseline to the intervention period (weeks 5 to 24 which excludes the 4-week ramp-up phase).

### *3.2 Secondary outcomes*

Secondary outcomes include the proportion of participant-days that step goals are achieved during the intervention and follow-up periods, and change in daily steps from baseline to the follow-up period.

### *3.3 Exploratory outcomes*

We will explore how participant characteristics and behaviors are associated with strong or poor physical activity performance.

## **4. Background**

Regular physical activity is associated with reduced risk for cardiovascular disease, diabetes, hypertension, and obesity. Less than half of adults in the United States, however, achieve enough physical activity to obtain these benefits. Digital health approaches that use engagement strategies such as gamification are commonly found within workplace wellness programs and mobile applications, but the evidence on their effectiveness is limited. Our prior work has demonstrated that insights from behavioral economics can be used to design interventions to address predictable barriers to behavior change.

Social incentives or those influences that impact individuals to adjust their behaviors based on social ties and connections have been demonstrated in retrospective studies to influence behavior but have not been well examined prospectively. Insights from behavioral economics can be used to design gamification interventions to enhance social incentives such as the support, competition, or collaboration but the optimal design to increase physical activity is unknown.

## **5. Study design**

### *5.1 Design*

This is a four-arm randomized, controlled trial with a 24-week intervention period and 12-week follow-up period. The study will be conducted using Way to Health, a research information technology platform at the University of Pennsylvania used previously for physical activity behavioral interventions.

Recruitment will occur by email invitation to employees in the United States at Deloitte, a large consulting company. Interested participants will be instructed to visit the study website to create an account, review and provide informed consent, and complete a baseline eligibility survey. Eligible participants will also be asked to complete a custom sociodemographic survey; the DOSPERT survey to evaluate risk preferences; the Big Five Inventory survey to evaluate personality characteristics; and the Grit Scale to assess perseverance at the time of enrollment. At 0 and 6 months, participants will be asked to complete an EQ-5D-5L survey for economic evaluation of health status, the Self Efficacy for Exercise Behaviors survey, the Eating Habits Questionnaire, the Pittsburgh Sleep Quality Index, the PHQ-9 questionnaire to assess mental health state, the MOS Social Support survey, and a qualitative survey to provide feedback on their experience in the study. Once surveys are completed in enrollment, a wearable activity tracking device will be mailed to the participant and they will be told to wear the device during day and night to get accustomed to it during a 2-week run-in period. Data collected from this time will be used to estimate a baseline step count by using data from the second week (days 8 to 14), ignoring values less than 1000 steps (since evidence suggests these value are unlikely to represent actual activity). Participants without at least 4 days of data will be called to inquire if

there are any issues with using the device and the period will be extended until at least 4 days of data are available to estimate a baseline step count.

Participants that have been confirmed by the study team to have an appropriate baseline step count will be asked to select a step goal increase as follows:

### **--Goal Setting--**

Each participant will be asked to choose a step goal increase that is either 33%, 40%, or 50% higher than baseline (each step goal will be rounded up to the nearest hundred). A participant may also select to choose another goal as long as it is at least 1500 steps greater than his or her baseline.

### **--Randomization—**

Participants are considered ready to be randomized once they have completed all surveys, established a baseline step count, and selected a step goal increase.

Participants will be stratified on baseline step count (less than 5000 steps, 5001 to 7500 steps, or more than 7500 steps). Participants will then be randomly assigned within their strata in blocks of four groups, with each group having 3 participants. The first participant in the group will be randomly assigned to the arm and the next 2 participants will be assigned to fill that group. Then the next participant will be randomly assigned to an arm within that block and the following two participants will be assigned to fill that group, and so on until the block within the strata is filled of 4 groups, each with three participants per group.

Participants in all arms will be asked to complete a series of follow-up surveys the end of the 24-week intervention period and again at the end of the 12-week follow up period. The interventions within each arm are as follows:

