### **--Arm 2-4: social incentive-based gamification interventions--**

Participants randomized to the one of the three intervention arms will have a 4-week ramp up towards their step goal (the “ramp-up period). The net difference between baseline and their goal will be divided by 4 and the participant will be asked to achieve the 25% increase each week for the 4-week ramp-up and then maintain the step goal for the remaining study period. For example, a participant with a baseline of 6000 steps and goal of 8000 steps will be asked to achieve goals of 6500, 7000, 7500, and 8000 for each of the first four weeks of the study. The participant will be asked to maintain their goal (e.g. 8000 steps per day) during the 20-week “maintenance period” and the 12-week “follow-up period”

Participants in arms 2-4 will be entered into an intervention approach that has points and levels designed to incorporate insights from behavioral economics. First, participants will be asked to sign a pre-commitment pledge to strive to achieve their step goal during the 36-week study. Pre-commitment has been demonstrated to motivate behavior change. Second, at the beginning of each week the participant receives 70 points (10 for each day that week). If the participant does not achieve their step goal, they lose 10 points from their balance. This leverages loss aversion, which has been demonstrated to motivate behavior change more effectively with losses than gains. Third, at the end of each week if the participant has at least 40 points, he or she will move up a level (levels from lowest to highest: blue, bronze, silver, gold, platinum). If not, participants will drop a level. All participants begin at the silver level. Each week, participants get a fresh set of 70 points on Monday.

At 8 and 16 weeks, participants struggling to meet their goals (defined as in the blue or bronze levels of the game) will be contacted to inquire about their progress in the study. They will be reset to the silver level and given the opportunity to readjust their goals among the initial options.

Weekly feedback will differ among the three arms to induce the different social incentives (support, competition, and collaboration) as follows:

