**--Arm 3: Competitive social incentive intervention--**

Participants in this arm will be in a group of three total participants. At the end of each week the participants will receive an email with a leaderboard that ranks them on their cumulative points in the study thus far and also displays their level. In the event there is a tie in total cumulative points, the participants will be secondarily ranked on level. This feedback may help to induce participants to compete for the top spot among the group.

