**--Arm 4: Collaborative social incentive intervention--**

Participants in this arm will be in a group of three total participants as a team. Each day one of the members of the group will be randomly selected to represent their team for that day. If the participant selected met his or her step goal on the previous day, the team keeps their points. If he or she didn't meet their goal, then the team loses 10 points. In this design, each person is accountable to the others on the team and this may induce a collaborative effort to meet their daily goals. The entire team moves up a level only if the team has at least 40 points by the end of the week.

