### *5.4 Accrual*

This study has been powered for two phases of hypothesis testing. In the first phase, we will compare each of the three intervention arms to control. We estimate that a sample of 600 participants allocated in a 1:1:1:1 distribution, will ensure at least 80% power to detect an 800 step difference between each intervention arm and control, with a standard deviation of 2000 steps. This calculation assumes a 10% dropout rate and a conservative Bonferroni adjustment of the type I error rate with a 2-sided alpha of 0.017. In the second phase, we will compare successful intervention arms to each other. We expect that the magnitude of difference between intervention arms will be less than that of successful intervention arms compared to control. For this second phase of analyses will use a conservative Bonferroni adjustment of the type I error rate with a 2-sided alpha of 0.017 to adjust for up to 3 comparisons. Because only intervention arms which demonstrated a significant difference with the control are compared with each other in the second phase, the overall familywise error rate of this two-phase procedure is controlled at 0.05.

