## **7. Subject compensation**

All participants will receive \$25 to enroll in the study (defined as being randomized and starting the intervention), \$50 for completing the 24-week intervention and surveys, and \$50 for completing the entire 36-week study.

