## **9. Analysis plan**

All analyses will be performed using intention-to-treat. Data can be missing for any day if the participant did not use the activity tracking device or did not upload data. For the main analysis, we will use multiple imputation for step values that are either missing or for values less than 1000 steps because evidence suggests these are not accurate measures of actual activity. We will perform five sets of imputations and results will be combined using Rubin's standard rules. We will perform sensitivity analyses to assess the robustness of the findings using only collected data with and without step values less than 1000 steps.

The primary analysis will fit mixed effects regression models to evaluate changes in physical activity outcomes measures adjusting for each participant's baseline step, time at the observation level using calendar month fixed effects, participant random effects, and adjusting for repeated observations of participant step counts. We will compare changes from baseline to the intervention period (excluding weeks 1 to 4 during the ramp-up phase) and from baseline to the follow-up period. Secondary analyses will fit mixed effects regression models adjusted for other variables of interest such as participant characteristics. Exploratory analyses will fit mixed effects regression models to evaluate associations of participant characteristics or behaviors with strong or poor performance in the outcome measures. We will also conduct an exploratory qualitative evaluation of the survey free text responses.

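### Trios are the randomised unit and interact in arms 3 and 4, but the primary model and the power calculation treat participants as independent

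*Combined protocol and SAP*

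**What the plan says.** All references are to the combined protocol and SAP.

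- **Section 5.1, Randomization.** Within each baseline-step stratum, the "first participant in the group will be randomly assigned to the arm and the next 2 participants will be assigned to fill that group". Blocks hold four such groups of three. The rule applies to all four arms.
- **Section 5.1, Arm 3.** Feedback is weekly: "the participants will receive an email with a leaderboard that ranks them on their cumulative points in the study thus far". The ranking is among the three members of the group.
- **Section 5.1, Arm 4.** "Each day one of the members of the group will be randomly selected to represent their team for that day". If that member missed the goal, the whole team loses points, and the team changes level together.
- **Section 5.1, Arms 1 and 2.** Control participants receive no intervention. Each arm 2 participant is supported by a relative or friend of their own. Neither arm's text gives the trio any role after assignment.
- **Section 9.** The primary model adjusts for baseline steps and calendar month, with "participant random effects, and adjusting for repeated observations of participant step counts". It has no trio term and no clustered variance.
- **Section 5.4, repeated in section 9.** A sample of 600, allocated 1:1:1:1, "will ensure at least 80% power to detect an 800 step difference between each intervention arm and control", with SD 2000, 10% dropout and two-sided alpha 0.017. No ICC or design effect is given. Both sections also say that the two-phase procedure controls the familywise error rate at 0.05.

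**The concern.** A participant random effect handles correlation among one person's daily step counts. It does nothing for correlation between the three people who share a draw. In arms 3 and 4 such correlation is what the intervention is meant to create: members are to influence each other's steps, and steps are the primary outcome. Baseline steps and calendar month do not absorb that influence.

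If the correlation is positive, a model without the trio understates the standard error of every comparison involving arm 3 or 4. The test at 0.017 then rejects too often, and the familywise claim, which rests on those tests, is no longer exact. The comparison of arm 3 with arm 4 is the most exposed, because both sides are clustered. If the correlation is negative, as ranking members against each other could produce in arm 3, the error runs the other way and the test is conservative. In either case the stated precision is not the real one.

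**Working it through.** **1. Reproduce the plan's figure, assuming independent participants.** Inputs from section 5.4: difference 800, SD 2000, two-sided alpha 0.017 (z = 2.387), power 80% (z = 0.842), 10% dropout, 600 participants.

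- n per arm = 2 × (2.387 + 0.842)² × 2000² / 800² = 130.3, so 131. With dropout, 131 / 0.9 = 145.6, so 146 per arm and 584 in all. The plan's 600 covers this.
- Power with 600: n = 150 × 0.9 = 135 per arm; SE = 2000 × √(2/135) = 243.4; 800 / 243.4 = 3.286; Φ(3.286 − 2.387) = 81.6%.

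The plan's figure is right on its own assumption. The margin over 80% is 1.6 points.

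**2. Add the trio.** The ICC here is the correlation of participants' mean change within a trio. The documents give none, so the values below are assumptions. With trios of three, the design effect in a clustered arm is D = 1 + 2 × ICC. Control and arm 2 members do not interact, so they are given D = 1.

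- Arm 3 or 4 against control (or against arm 2): average design effect = (D + 1) / 2 = 1 + ICC.
- Arm 3 against arm 4: average design effect = D = 1 + 2 × ICC.
- Power with a correct standard error = Φ(800 / (243.4 × √average) − 2.387).
- Actual error if the trio is ignored = 2 × (1 − Φ(2.387 / √average)).

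| Assumed ICC | SE, arm 3 or 4 v control | Power v control | Actual error v control | Actual error, arm 3 v arm 4 |
|---|---|---|---|---|
| 0 | 243.4 | 81.6% | 0.017 | 0.017 |
| 0.02 | 245.9 | 80.7% | 0.018 | 0.019 |
| 0.05 | 249.4 | 79.4% | 0.020 | 0.023 |
| 0.10 | 255.3 | 77.2% | 0.023 | 0.029 |

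A simulation of 45 trios per arm (20,000 runs) gave 0.0190 and 0.0232 against control at ICC 0.05 and 0.10, close to the formula. With 10% random dropout the trios are slightly smaller and D is nearer 1 + 1.8 × ICC; power at 0.05 is then 79.6%.

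**3. Where 80% power is lost.** The SE may be at most 800 / (2.387 + 0.842) = 247.8. The average design effect may then be at most (247.8 / 243.4)² ≈ 1.036, so the ICC may be at most about 0.036.

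**4. Familywise error.** Arm means were simulated (four million draws) with variance inflated by D in arms 3 and 4 only, each pair being tested at 0.017 with the uninflated SE.

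| Assumed ICC | Phase one, no arm effective | Phase two, all three arms equally effective and past phase one |
|---|---|---|
| 0 | 0.045 | 0.045 |
| 0.02 | 0.048 | 0.048 to 0.049 |
| 0.05 | 0.050 to 0.051 | 0.054 to 0.055 |
| 0.10 | 0.056 | 0.064 to 0.065 |

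Ranges show the spread between repeat runs.

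**5. Negative correlation in arm 3.** At ICC −0.05 in that arm alone, D = 0.9 and the average is 0.95. The actual error against control is 2 × (1 − Φ(2.387 / √0.95)) = 0.014, below nominal.

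**The case against.** The best defence is that the effect is small. An ICC of 0.05 in the intervention arm costs as much power as an SD of 2000 × √1.05 = 2049 in place of 2000, well within the uncertainty of the planning SD. At ICC 0.02 the familywise rate is still below 0.05 in both phases, because tests that share an arm are correlated and Bonferroni leaves some slack. Arm 2 against control is essentially untouched. All of this stands. It limits the size of the problem, but it does not justify leaving out the trio: the ICC is unknown, the design aims to create it, and allowing for it costs almost nothing.

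Three stronger readings are tempting, and the documents do not support them.

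- **That allocation was unconcealed and open to selection bias.** Since two of every three assignments follow the first, a reader might infer that staff could foresee them. Staff do act before randomisation: "Participants that have been confirmed by the study team to have an appropriate baseline step count will be asked to select a step goal". But the text does not say when a first member's arm is released or who sees running assignments. Foresight needs an observer whom no section describes. This is missing detail, not a described defect.
- **That power is 77.2% at ICC 0.05 and 73.0% at 0.10.** Those figures inflate the control arm as well, although control participants do not interact.
- **That familywise error reaches 0.057 or 0.063.** Those are Bonferroni sums (0.017 + 2 × 0.0198 and 0.017 + 2 × 0.0229). They ignore the shared control arm and overstate the simulated phase-one rates.

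**Conclusion.** The point holds for the analysis and the power statement. The randomised unit, which is also the interacting unit in arms 3 and 4, is absent from both. Standard errors for comparisons involving those arms will be wrong if outcomes within trios are correlated, and the direction depends on the sign of the correlation.

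The size is modest and rests on an assumed ICC. Between 0.05 and 0.10, per-comparison error is about 0.020 to 0.023 against control and 0.023 to 0.029 for arm 3 against arm 4. The familywise claim is barely exceeded at the lower value and clearly exceeded at the upper. The claim of at least 80% power fails for arms 3 and 4 once the ICC passes about 0.036. These figures assume no trio correlation in control and arm 2. Consecutive enrolment could produce a little there, part of which the calendar-month terms would absorb.

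The plan should be changed. Nothing here shows that the sample size was miscalculated on its own assumptions, or that the randomisation is biased.

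**What to change.** - **Section 9.** Keep the participant random effects and base inference for the primary and phase-two comparisons on standard errors clustered by trio, computed in each imputed data set before pooling. There are about 600 / 3 = 200 trios, 50 per arm, which is ample. Clustered standard errors are the better choice because they remain valid for negative correlation. An ordinary trio random effect, whose variance cannot be below zero, cannot represent that. If a trio random effect is used instead, let its variance differ by arm.
- **Section 5.4 and its repeat in section 9.** State the power for arms 3 and 4 against control as a range over an assumed ICC, for example 81.6% at 0, 80.7% at 0.02, 79.4% at 0.05 and 77.2% at 0.10. Leave arm 2 against control near 81.6%. Do not enlarge the sample.
- **Section 5.1, Randomization (clarification only).** Add one sentence saying that running assignments are not visible to staff who confirm baselines or call participants before randomisation.

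The cost is one change to the variance estimate, some wording, and a slightly less favourable stated power.

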### **--Arm 1: Control—**

Participants in this arm will receive no other interventions during the 24-week intervention period or the 12-week follow-up period.

### **--Arm 2-4: social incentive-based gamification interventions--**

Participants randomized to the one of the three intervention arms will have a 4-week ramp up towards their step goal (the “ramp-up period). The net difference between baseline and their goal will be divided by 4 and the participant will be asked to achieve the 25% increase each week for the 4-week ramp-up and then maintain the step goal for the remaining study period. For example, a participant with a baseline of 6000 steps and goal of 8000 steps will be asked to achieve goals of 6500, 7000, 7500, and 8000 for each of the first four weeks of the study. The participant will be asked to maintain their goal (e.g. 8000 steps per day) during the 20-week “maintenance period” and the 12-week “follow-up period”

Participants in arms 2-4 will be entered into an intervention approach that has points and levels designed to incorporate insights from behavioral economics. First, participants will be asked to sign a pre-commitment pledge to strive to achieve their step goal during the 36-week study. Pre-commitment has been demonstrated to motivate behavior change. Second, at the beginning of each week the participant receives 70 points (10 for each day that week). If the participant does not achieve their step goal, they lose 10 points from their balance. This leverages loss aversion, which has been demonstrated to motivate behavior change more effectively with losses than gains. Third, at the end of each week if the participant has at least 40 points, he or she will move up a level (levels from lowest to highest: blue, bronze, silver, gold, platinum). If not, participants will drop a level. All participants begin at the silver level. Each week, participants get a fresh set of 70 points on Monday.

At 8 and 16 weeks, participants struggling to meet their goals (defined as in the blue or bronze levels of the game) will be contacted to inquire about their progress in the study. They will be reset to the silver level and given the opportunity to readjust their goals among the initial options.

Weekly feedback will differ among the three arms to induce the different social incentives (support, competition, and collaboration) as follows:

